4.6.1.5.2 Pharmacokinetic Assessments

Blood and urine samples will be collected to evaluate the PK of RO7062931 and metabolites as specified in the SoA (see [Appendix 1](#) to [Appendix 14](#)). When the PK assessment is scheduled for the same nominal time as another scheduled assessment, the PK blood samples should be taken as close as possible to the scheduled time.

Blood and urine samples will be collected from all healthy volunteer cohorts in Part 1 and from CHB patients in Part 2. The volume of each urine sample at each interval will be measured by the site staff and recorded in CRF. The actual date and time of each blood sample collection, the start and end date and time for each urine sample collection will be recorded in CRF.

[REDACTED]

Sparse sampling for tenofovir (including tenofovir alafenamide, if approved for HBV and applicable), entecavir, adefovir and telbivudine will be collected *for Parts 2a and 2b and entecavir, tenofovir alafenamide, or tenofovir disoproxil fumarate for Part 2c.*

A decision to stop PK sampling earlier or to collect more samples than currently proposed scheduled times will be based on the PK profile of the study drug. Timing of PK sampling may change based on emerging PK results after agreement with the Sponsor and the Investigator.

PK parameters will be estimated using standard non-compartmental methods for RO7062931.

PK samples will be stored for up to 2 years for the protocol assessments, unless otherwise indicated. Samples will be destroyed no later than 2 years after the date of final closure of the clinical database, unless regulatory authorities require specimens to be maintained for a longer time period. If required, the residual of the PK samples taken during the study (any time-point) can be used for additional analysis (including assay validations and immunogenicity analyses).

Additional PK samples will also be collected at the time of a serious adverse event.

Samples for laboratory tests as specified above will be sent to one or several central laboratories or to the Sponsor for analysis. For sampling procedures, storage conditions, and shipment instructions, see the separate laboratory manual.

4.6.1.5.3 Assessments for Inflammatory Markers, Autoantibodies and Anti-Drug Antibodies (ADA)

Samples for laboratory tests as specified below will be sent to one or several central laboratories or to the Sponsor for analysis. For sampling procedures, storage conditions, and shipment instructions, see the separate laboratory manual.

Handling of residual samples is described in Section [4.6.1.5](#).

The following separate assessments will take place in this study:

- For inflammatory markers
- For development of autoantibodies
- For development of anti-drug antibodies (ADAs)

Inflammatory Markers

Blood samples for assessing inflammatory markers will be obtained for all study subjects at pre-specified time-points (see SoA, [Appendix 1](#) to [Appendix 14](#)). In addition, in case an immune driven AE/AE suggestive of immunological involvement occurs, an unscheduled sample will be collected as close to the onset of the AE as possible. Blood samples (both planned and unscheduled) will be taken to assess: complement, CRP, ESR, gamma globulin and other inflammatory biomarkers (such as, but not limited to, IL-6, IL-8, IL12, MCP1, TNF α).

For patients in Part 2c, a baseline (Day 1, pre-dose) sample for inflammatory markers will be assessed. In case an immune AE/AE suggestive of immunological involvement occurs, the samples collected at the other time-points as well as an unscheduled sample collected as close to the onset of the AE as possible will be assessed.

Auto-antibodies

Blood samples for assessing autoantibodies will be obtained for all study subjects before dosing, at baseline (also see SoA, [Appendix 1](#) to [Appendix 14](#)). In addition, in case of an autoimmune driven AE/AE suggestive of autoimmunological involvement occurs, an unscheduled sample will be collected as close to the onset of the AE as is possible. The panel of autoantibodies to be assessed will be: anti-nuclear antibodies, anti-ds-DNA antibodies, anti-histone antibodies, anti-ssDNA antibodies, anti-neutrophil cytoplasmic antibody, anti-cardiolipin antibodies, *and* rheumatoid factor.

ADA Assessment

Blood samples will be collected from all subjects at each time-point as specified in the SoA tables (see [Appendix 1](#) to [Appendix 14](#)). All ADA blood samples *will* be collected prior to dosing of investigational drug.

4.6.1.5.4 Pharmacodynamic Assessments

During the course of the study, PD sampling time-points may be modified on the basis of emerging data to ensure the pharmacodynamics of RO7062931 can be adequately characterized.

Blood samples for pharmacodynamics assessments will be collected as indicated in the SoA tables (see [Appendix 1](#) to [Appendix 14](#)). Samples for laboratory tests as specified below will be sent to one or several central laboratories or to the Sponsor for analysis. For sampling procedures, storage conditions, and shipment instructions, see the separate laboratory manual.

In Part 2c, based on continuous analysis of the data in this study and other studies, any sample type not considered to be critical for PD evaluation may be stopped at any time if the data from the samples collected does not produce useful information.

Handling of residual samples is described in Section [4.6.1.5](#).

HBV-Specific Viral Assessments

HBV-specific viral assessments will be performed only in patients in Part 2 of the study; also see viral dynamic outcome measures in Section [3.3.2.2](#). Monitoring of viral resistance will be performed in any patient that experiences breakthrough.

Commercially available assays will be used for the assessment of viral parameters when available and applicable. For the parameters that do not have suitable commercial assays, validated research type assays will be used.

Blood samples for viral dynamic data and viral genotyping will be collected.

Viral Resistance Monitoring

Blood samples will be collected at baseline (BL; Day 1 pre-dose) and throughout the study, as detailed in the SoA, to monitor for the development of drug resistance. Sequencing of the complete HBV genome will be performed for all viral resistance monitoring samples at BL if viral load is ≥ 1000 copies/mL. For patients whose BL sample contains < 1000 copies/mL and therefore, a BL sequence cannot be established, an archived sample should be provided with a reasonable effort if available in order to get a BL sequence. If a patient experiences an increase in serum HBV DNA level of more than $1\log_{10}$ (10-fold) over nadir (viral breakthrough) during the treatment period or follow-up period of the study, an ad hoc (unscheduled) blood sample will be taken to confirm the breakthrough. Samples from confirmed viral breakthrough and subsequent follow-up visits will be sent for population sequencing. Other sequencing analyses (e.g., ultra deep sequencing) and phenotypic analysis may be performed in addition.

Virological breakthrough should be reported as an adverse event.

4.6.1.5.5 Clinical Genotyping

A blood sample will be taken pre-dose on Day 1 for DNA extraction from all subjects. If, however, the genetic blood sample is not collected during the scheduled visit, it may be collected at any time during the conduct of the clinical study. [REDACTED]

[figure not shown]
The sample collected for DNA extraction may be used for whole exome and/or whole genome sequencing and other genetic analysis and may be sent to one or more laboratories for analysis. These assessments will be performed if safety or scientific rationales develop.

Handling of residual samples is described in Section [4.6.1.5](#).

Data arising from clinical genotyping will be subject to the confidentiality standards described in Section [8.4](#).

4.6.1.5.6 Other Assessments

A number of exploratory safety urinary kidney biomarkers will be analyzed from urine samples including but not limited to: α 1-microglobulin, β 2-microglobulin, and KIM-1.

Based on continuous analysis of the data in this study and other studies, any sample type not considered to be critical for safety evaluation may be stopped at any time if the data from the samples collected does not produce useful information.

Samples as specified above will be sent to one or several central laboratories or to the Sponsor for analysis. For sampling procedures, storage conditions, and shipment instructions, see the separate laboratory manual.

Handling of residual samples is described in Section [4.6.1.5](#).

4.6.1.5.7 Optional Samples for Research Biosample Repository

Overview of the Research Biosample Repository

The Roche Research Biosample Repository (RBR) is a centrally administered group of facilities for the long-term storage of human biologic specimens, including body fluids, solid tissues, and derivatives thereof (e.g., DNA, RNA, proteins, peptides). The collection, storage and analysis of these specimens will facilitate the rational design of new pharmaceutical agents and the development of diagnostic tests, which may allow for individualized drug therapy for patients in the future.

Unused residual samples from the assessments described in Section [4.6.1.5.1](#) through to Section [4.6.1.5.6](#) will be retained as well as specimens will be collected from patients who give specific consent to participate in this optional Research Biosample Repository. Collected specimens will be used to achieve the following objectives:

- To study the association of biomarkers with efficacy, adverse events, or disease progression.
- To increase knowledge and understanding of disease biology.
- To study drug response, including drug effects and the processes of drug absorption and disposition.
- To develop biomarker or diagnostic assays and establish the performance characteristics of these assays.

Approval by the Institutional Review Board or Ethics Committee

Sampling for the RBR is contingent upon the review and approval of the exploratory research and the RBR portion of the Informed Consent Form by each site's Institutional Review Board or Ethics Committee (IRB/EC) and, if applicable, an appropriate regulatory body. If a site has not been granted approval for RBR sampling, this section of the protocol will not be applicable at that site.

Sample Collection

The following samples will be collected for identification of dynamic (non-inherited) biomarkers:

- Leftover serum and plasma samples to assess protein biomarkers including, but not limited to proteomics.

The following samples will be collected for identification of genetic (inherited) biomarkers:

- Blood for DNA extraction to assess for biomarkers, including but not limited to the following: single nucleotide polymorphisms (SNPs).

The samples collected for DNA extraction may be used for whole genome sequencing (WGS) and other genetic analysis and may be sent to one or more laboratories for analysis.

Genomics is increasingly informing researcher's understanding of disease pathobiology. WGS provides a comprehensive characterization of the genome and, along with clinical data collected in this study, may increase the opportunity for developing new therapeutic approaches. Data will be analyzed in the context of this study but will also be explored in aggregate with data from other studies. The availability of a larger dataset will assist in identification of important pathways, guiding the development of new targeted agents.

For all samples, dates of consent and specimen collection should be recorded on the associated RBR page of the eCRF. For sampling procedures, storage conditions, and shipment instructions, see the separate laboratory manual.

RBR specimens will be stored and used until no longer needed or until they are exhausted. The Research Biosample Repository storage period will be in accordance with the IRB/EC-approved Informed Consent Form and applicable laws (e.g., Health Authority requirements).

The repository specimens will be subject to the confidentiality standards (as described under Confidentiality and in Section 8.4).

Confidentiality

Data generated from RBR specimens must be available for inspection upon request by representatives of national and local Health Authorities, and Roche monitors, representatives, and collaborators, as appropriate.

Study subject medical information associated with RBR specimens is confidential and may only be disclosed to third parties as permitted by the Informed Consent Form (or separate authorization for use and disclosure of personal health information) signed by the study subject, unless permitted or required by law.

Data derived from RBR specimen analysis on individual study subject will generally not be provided to study investigators unless a request for research use is granted. The aggregate results of any conducted research will be available in accordance with the effective Roche policy on study data publication.

Genetic research data and associated clinical data may be shared with researchers who are not participating in the study or submitted to government or other health research databases for broad sharing with other researchers. Patients will not be identified by name or any other personally identifying information. Given the complexity and exploratory nature of these analyses, genetic data and analyses will not be shared with investigators or patients unless required by law.

Any inventions and resulting patents, improvements, and/or know-how originating from the use of the RBR specimen data will become and remain the exclusive and unburdened property of Roche, except where agreed otherwise.

Consent to Participate in the Research Biosample Repository

The Informed Consent Form will contain a separate section that addresses participation in the RBR. The Investigator or authorized designee will explain to each study subject the objectives, methods, and potential hazards of participation in the RBR. Study subjects will be told that they are free to refuse to participate and may withdraw their specimens at any time and for any reason during the storage period. A separate, specific signature will be required to document a study subject's agreement to provide optional RBR specimens. Study subjects who decline to participate will not provide a separate signature.

The Investigator should document whether or not the study subject has given consent to participate by completing the RBR Sample Informed Consent eCRF.

In the event of death or loss of competence of a subject who is participating in the Research, the participant's specimens and data will continue to be used as part of the RBR.

Withdrawal from the Research Biosample Repository

Study subjects who give consent to provide specimens for the RBR have the right to withdraw their specimens at any time for any reason. If a study subject wishes to withdraw consent to the testing of his or her specimens, the Investigator must inform the Medical Monitor in writing of the study subject's wishes using the RBR Withdrawal Form and, if the trial is ongoing, must enter the date of withdrawal on the RBR Withdrawal of Informed Consent eCRF. The study subject will be provided with instructions on how to withdraw consent after the trial is closed. A study subject's withdrawal from Study BP39405 does not, by itself, constitute withdrawal of specimens from the RBR. Likewise, a study subject's withdrawal from the RBR does not constitute withdrawal from Study BP39405. Data already generated before time of withdrawal of consent to RBR will still be used.

Monitoring and Oversight

Specimens collected for the RBR will be tracked in a manner consistent with Good Clinical Practice by a quality-controlled, auditable, and appropriately validated laboratory information management system, to ensure compliance with data confidentiality as well as adherence to authorized use of specimens as specified in this protocol and in the Informed Consent Form. Roche monitors and auditors will have direct access to appropriate parts of records relating to study subject participation in Research Biosample Repository for the purposes of verifying the data provided to Roche. The site will permit monitoring, audits, IRB/EC review, and health authority inspections by providing direct access to source data and documents related to the samples.

4.6.2 Timing of Study Assessments

4.6.2.1 Screening and Pretreatment Assessments

Written informed consent for participation in the study must be obtained before performing any study-specific screening tests or evaluations. Informed Consent Forms for enrolled study subjects and for study subjects who are not subsequently enrolled will be maintained at the study site.

All screening and pre-treatment assessments must be completed and reviewed to confirm that study subjects meet all eligibility criteria. The Investigator will maintain a screening log to record details of all study subjects screened and to confirm eligibility or record reasons for screening failure.

An Eligibility Screening Form (ESF) documenting the Investigator's assessment of each screened study subject with regard to the protocol's inclusion and exclusion criteria is to be completed by the Investigator and kept at the investigational site.

For Part 2, documented liver biopsy or Fibroscan® or equivalent test results demonstrating chronic HBV infection with absence of cirrhosis and bridging fibrosis must be available within the 6 months. If no results are available, a Fibroscan® will be performed during screening.

If a subject fails an inclusion/exclusion criterion due to a transient and non-clinically significant condition at screening, the Investigator may repeat the relevant screening assessment(s) within the *screening period* (28 days for Part 1 and *Part 2c* and 56 days for *Parts 2a and 2b*). If the subject fails a second time, they will be classed as a screen failure and cannot be re-screened. Re-screening is allowed for subjects who were screened in the study and met study inclusion/exclusion criteria but failed to be randomized within 28 days after the start of *the* screening period for *Part 1 and Part 2c* or within 56 days after the start of *the* screening period for *Part 2a and 2b*. In order to re-screen such a subject, all inclusion and exclusion criteria should be re-evaluated and all applicable screening assessments repeated if done more than 28 days *before randomization* for Part 1 and *Part 2c* or more than 56 days *before randomization* for *Parts 2a and 2b*. There is no need to repeat alpha-fetoprotein test if done for the study in central laboratory within 6 months before re-screening.

4.6.2.2 Assessments during Treatment

Under no circumstances will study subjects who enroll in *any part* of this study and have completed treatment as specified, be permitted to be allocated a new randomization number and re-enroll in the study.

All assessments must be performed as per SoA tables (see [Appendix 1](#) to [Appendix 14](#)).

4.6.2.3 Follow-Up Assessments and Study Completion

Study subjects who complete the study or discontinue from the study early will be asked to return to the clinic after the last dose of study drug for a follow-up visit.

All follow up assessments must be performed as per SoA tables (see [Appendix 1](#) to [Appendix 14](#)).

Adverse events should be followed as outlined in Section [5.5](#).

4.7 SUBJECT, STUDY AND SITE DISCONTINUATION

4.7.1 Study Subject Discontinuation

Subjects will be treated until unacceptable toxicities or withdrawal of consent.

The Investigator has the right to discontinue a study subject from RO7062931 or withdraw a study subject from the study at any time. In addition, study subjects have the right to voluntarily discontinue study drug or withdraw from the study at any time for any reason. Reasons for discontinuation of study drug or withdrawal from the study may include, but are not limited to, the following:

- Study subject withdrawal of consent at any time.
- Any medical condition that the investigator or Sponsor determines may jeopardize the study subject's safety if he or she continues in the study.
- Investigator or Sponsor determines it is in the best interest of the study subject.

- Subject non-compliance.

4.7.1.1 Discontinuation from Study Drug

Study subjects must discontinue study drug if they experience any of the following:

- Pregnancy
- A serious adverse event (SAE) considered by the Investigator to be related to treatment with RO7062931.

Study subjects who discontinue study drug prematurely will be asked to return to the clinic for a study completion/early termination visit and may undergo follow-up assessments. The primary reason for premature study drug discontinuation should be documented on the appropriate eCRF.

Study subjects who discontinue study drug prematurely for safety reasons will not be replaced. Study subjects who discontinue study drug prematurely for non-safety reasons may be replaced. The Sponsor should be informed of subjects' discontinuations from the study or from the study drug.

Part 2: CHB Patients

Individual patients must discontinue RO7062931/placebo if they experience any of the following:

- Safety and tolerability issues, e.g., acute reactions, not tolerable and not manageable with symptomatic treatment.
- Grade 4 ALT (i.e., $\geq 10 \times \text{ULN}$) as defined by the Division of Acquired Immunodeficiency Syndrome (AIDS) Table for Grading the Severity of Adult and Pediatric Adverse Events ([DAIDS AE grading table](#)) confirmed within 48-72 hours (*not for Part 2c*).
- Grade 3 ALT (i.e., $> 5x$ to $< 10 \times \text{ULN}$) combined with total bilirubin $> 2 \times \text{ULN}$ (of which $> 35\%$ is direct bilirubin), or Grade 3 ALT and INR > 1.5 .
- Any other confirmed (within 48-72h) Grade 4 laboratory abnormality deemed clinically significant (based on Investigator's assessment).
- Development of liver decompensation (ascites, varices, Child-Pugh Class B or C clinical classification).
- *Grade 3 renal* adverse events defined as creatinine $\geq 50\%$ from baseline *and/or* *eGFR* $< 60 \text{ ml/min/1.73 m}^2$.
- Development of resistance in a CHB patient is suspected if the patient experiences an increase in serum HBV DNA of $> 1 \log_{10}$ (10-fold) over nadir during the treatment period, i.e., virological breakthrough.
- NUC analogue discontinuation due to safety issues or resistance development.

All prematurely discontinued patients will have assessments performed at the end of treatment with RO7062931/placebo listed in the SoAs tables. If a patient discontinues study drug between study visits, he/she should be called for an unscheduled visit to have these assessments performed.

All patients who discontinued the study treatment prematurely should complete the 4-week follow-up period (starting from the date of the last dose taken) *and continue safety follow up* as per SoAs (see [Appendix 1](#) to [Appendix 14](#)). The primary reason for premature study drug discontinuation should be documented on the appropriate eCRF.

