5.2.1.2 Alanine Transaminase (ALT) Elevations

Abrupt elevation of serum ALT above normal is known to occur spontaneously in patients with CHB during the course of disease, and/or during anti-viral therapy. Transient ALT elevations are not always harmful and may be due to:

- *The underlying disease*
- *Immune clearance of infected hepatocytes*
- *Drug-induced immune-mediated hepatitis*
- *DILI*

Isolated ALT elevations of 2-3 times the baseline value that are self-limited may reflect a desirable treatment-related immunologic response rather than drug toxicity. However, progressive increases or ALT elevations associated with increases in bilirubin without alkaline phosphatase increase should primarily be considered adverse events, i.e. potential DILI.

In the event of ALT elevation > 5x ULN, more frequent monitoring of liver tests should be performed based on medical judgment and other causes of ALT elevations should be investigated. For patients with ALT > 5 × ULN, the following management plan is recommended:

ALT elevations during treatment

- *Isolated ALT elevation with preserved hepatic function (e.g. no significant changes in bilirubin, INR/PT, albumin, and ALP):*
 - *Closely monitor liver function tests (LFTs) (i.e. ALT/AST, bilirubin, albumin, ALP and INR/PT):*
 - *ALT 5 to 10 x ULN: Repeat LFTs every week.*
 - *ALT >10 x ULN: Temporarily interrupt RO7062931 or RO7062931 and PEG-IFN treatment and repeat LFTs twice weekly until ALT level < 5 x ULN. Continue NUC treatment. Consider re-introducing RO7062931 or RO7062931 and PEG-IFN therapy following discussion with medical monitor based on subsequent laboratory results.*
- *ALT flare accompanied by declining liver synthetic and excretory functions (increased bilirubin >2 x ULN, or albumin decline >0.5 g/dL, or INR >1.5) or other signs of hepatic impairment (severe fatigue, nausea, vomiting, right upper quadrant pain):*
 - *RO7062931 or RO7062931 and PEG-IFN will be permanently discontinued, continue NUC treatment.*
 - *Closely monitor liver function tests:*
 - *ALT 5 to 10 x ULN: Repeat LFTs every week.*
 - *ALT >10 x ULN: Repeat LFTs twice weekly until ALT level < 5 x ULN.*
 - *Investigate the participant for potential etiologies of the laboratory changes.*
 - *If alternative reasons/diagnoses cannot explain the laboratory changes, a potential DILI will be considered.*

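### In Part 2c the ALT bullets of the mandatory stopping list (4.7.1.1) end at ALT <10 × ULN, out of step with the flare rule in 5.2.1.2: a drafting inconsistency with limited practical risk

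*Combined protocol and SAP*

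**What the plan says.** Section 4.7.1.1 lists findings after which a Part 2 patient must come off RO7062931 or placebo. Two bullets concern ALT.

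- The first stops for Grade 4 ALT, given as 10 × ULN or more. It carries the qualifier "confirmed within 48-72 hours (*not for Part 2c", so Part 2c is exempt.
- The second stops for Grade 3 ALT, defined in the bullet as above 5 and below 10 × ULN, with total bilirubin above 2 × ULN of which more than 35% is direct, "or Grade 3 ALT and INR > 1.5".

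The same section also requires a stop for:

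- "A serious adverse event (SAE) considered by the Investigator to be related to treatment with RO7062931";
- any other confirmed "Grade 4 laboratory abnormality deemed clinically significant";
- liver decompensation, including Child-Pugh B or C;
- safety problems that are neither tolerable nor manageable.

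Section 5.2.1.2 covers ALT above 5 × ULN and opens with "the following management plan is recommended". It has two branches during treatment.

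- Isolated ALT above 10 × ULN with preserved liver function: "Temporarily interrupt RO7062931 or RO7062931 and PEG-IFN treatment", with liver tests twice weekly and re-introduction considered after discussion with the medical monitor.
- ALT flare with bilirubin above 2 × ULN, an albumin fall of more than 0.5 g/dL, INR above 1.5, or clinical signs of hepatic impairment: "RO7062931 or RO7062931 and PEG-IFN will be permanently discontinued, continue NUC treatment". This branch has its own monitoring line, "ALT >10 x ULN: Repeat LFTs twice weekly until ALT level" is below 5 × ULN, so it has no upper ALT limit.

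**The concern.** In Parts 2a and 2b the upper limit on the combined stop does no harm, because the Grade 4 bullet takes over at 10 × ULN. In Part 2c that bullet is waived and nothing replaces it. With the same abnormal INR, or the same bilirubin that is more than 35% direct, ALT of 9.9 × ULN is a mandatory stop on the ALT bullets and ALT of 12 × ULN is not. The combined bullet cannot be read as Grade 3 or higher, because it states its own upper limit.

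A site working from the mandatory list and one working from the management plan should reach the same decision on the same liver results. Part 2c gives weekly RO7062931 for up to 48 weeks, with PEG-IFN in Cohort 10, and the protocol expects ALT flares. The synopsis also counts discontinuations due to adverse events among the safety endpoints, and that count should not depend on which section a site consulted.

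**Working it through.** There is no stated figure to reproduce. The check compares the rules case by case.

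**Rules, with ALT and bilirubin in multiples of ULN**

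- 4.7.1.1, combined bullet: 5 < ALT < 10 and ((bilirubin > 2 and direct > 35%) or INR > 1.5).
- 4.7.1.1, Parts 2a/2b: the combined bullet, or ALT ≥ 10 (if confirmed).
- 4.7.1.1, Part 2c: the combined bullet only.
- 5.2.1.2 permanent stop: ALT > 5 and (bilirubin > 2, or INR > 1.5, or albumin fall > 0.5 g/dL). The clinical-signs trigger is left out of the grid.

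**Grid.** ALT is 6, 9.9, 10, 12 and 20. Each cell counts how many of the five ALT values give a stop.

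| Other finding | 4.7.1.1, 2a/2b | 4.7.1.1, 2c as written | 5.2.1.2 permanent stop | 4.7.1.1, 2c with upper limit removed | 4.7.1.1, 2c with limit removed and flare bullet added |
|---|---|---|---|---|---|
| Bilirubin 3, 50% direct | 5 | 2 (ALT 6, 9.9) | 5 | 5 | 5 |
| INR 1.8 only | 5 | 2 (ALT 6, 9.9) | 5 | 5 | 5 |
| Bilirubin 3, 20% direct | 3 (ALT 10, 12, 20) | 0 | 5 | 0 | 5 |
| Albumin fall 0.6 g/dL only | 3 (ALT 10, 12, 20) | 0 | 5 | 0 | 5 |
| None (isolated ALT) | 3 (ALT 10, 12, 20) | 0 | 0 (interrupt at 12 and 20) | 0 | 0 |

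The first two rows are the direct test of the combined bullet. Part 2c meets 2 + 2 = 4 of 10, none of them at ALT ≥ 10. Parts 2a/2b and 5.2.1.2 each meet 10 of 10.

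Rows three and four show a second mismatch. Section 5.2.1.2 has no direct-bilirubin condition and has an albumin trigger that 4.7.1.1 lacks. Removing the upper limit alone would leave both rows in conflict.

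The last row shows that the correction keeps the purpose of the waiver. It also shows two smaller mismatches. In Parts 2a/2b, confirmed isolated ALT ≥ 10 is a mandatory stop in 4.7.1.1, while 5.2.1.2, which is not limited to Part 2c, allows re-introduction. At exactly 10, 4.7.1.1 uses ≥ and 5.2.1.2 uses >.

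**Other mandatory routes for Part 2c cases at ALT ≥ 10**

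- Potential DILI (5.2.1.1) needs ALT > 3 × the higher of baseline and ULN, bilirubin > 2 × ULN and no other apparent cause. It must be reported as an SAE. In Cohorts 9 and 10 screening ALT is at most 2 × ULN. If that holds at baseline, the threshold is at most 3 × 2 = 6 × ULN. Bilirubin cases at ALT 10, 12 and 20 qualify (3 of 3 if no other cause is apparent); INR-only cases do not (0 of 3). The mandatory stop then needs the investigator to judge the SAE related.
- Child-Pugh (Appendix 16), with encephalopathy and ascites at 1 point each: total = 2 + bilirubin + albumin + prothrombin scores. Class A (total ≤ 6) remains in 4 of 27 score patterns: all three at 1, or exactly one at 2. INR-only with prothrombin prolonged 4–6 s scores 1 + 1 + 1 + 1 + 2 = 6 (A); above 6 s it scores 7 (B). Bilirubin 2–3 mg/dL plus 4–6 s scores 1 + 1 + 2 + 1 + 2 = 7 (B).
- Raised bilirubin alone reaches Class B only above 3 mg/dL. The documents give no bilirubin ULN. Assuming 1.0, 1.2 or 1.5 mg/dL, 3 mg/dL is 3.0, 2.5 or 2.0 × ULN, so the range not caught is >2 to 3.0 × ULN, >2 to 2.5 × ULN, or none.

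**The case against.** The strongest reply is that the protocol, read as a whole, already stops these patients. Section 4.7.1.1 never tells a site to continue drug at ALT ≥ 10 × ULN with raised bilirubin or INR. The operative line in 5.2.1.2 is firm although its lead-in is soft, and it names ALT above 10 × ULN. Even a case misread as isolated would be interrupted above 10 × ULN, with twice-weekly liver tests and discussion with the medical monitor before any restart; only ALT of exactly 10 escapes the hold. Isolated ALT of 10 × ULN or more is also an event of special interest, reportable within 24 hours (5.1.3). This reply stands, and it is why the risk is limited.

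It is also fair that the grid shows where the rules diverge, not how often patients would fall there. The ALT values and the direct-bilirubin percentages were chosen for illustration.

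The reply does not remove the mismatch. A list headed as mandatory should not drop the more severe case, and 5.2.1.2 refers back to 4.7.1.1 only for decompensation.

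Three stronger readings are tempting, and the documents do not support them.

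- A reader might infer that Part 2c patients with severe flares have no firm stop, or one found only in a plan labelled as a recommendation. Besides 5.2.1.2, section 4.7.1.1 mandates stopping for a related SAE, Child-Pugh B or C, and intolerable safety issues.
- A reader might infer that the Grade 4 waiver is itself a mistake. It agrees with the interrupt-and-reconsider rule for isolated ALT in 5.2.1.2.
- A reader might infer a DILI threshold of 15 × ULN (3 × 5) in treatment-naïve cohorts. Section 5.3.5.6 caps that ALT threshold at 10 × ULN. The cap is written for adverse event reporting and may or may not govern 5.2.1.1, so no shortfall is claimed.

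**Conclusion.** The point holds as an inconsistency between two sections, confined to the ALT bullets of 4.7.1.1 in Part 2c. ALT ≥ 10 × ULN with bilirubin above 2 × ULN or INR above 1.5 meets neither bullet, while ALT above 5 and below 10 × ULN with the same INR, or with the same bilirubin more than 35% direct, does. It is a drafting fault in a safety rule, not an absence of protection. The remaining mandatory routes are partial or depend on judgement, and the clearest residue is INR-only cases that stay Child-Pugh A.

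The finding about the bullets rests on their text alone. The account of what other routes catch assumes baseline ALT within the screening limit in Cohorts 9 and 10 and, for raised bilirubin alone, an assumed ULN. How often such cases would occur cannot be estimated from the documents. The correction is worth making because it is small and follows the sponsor's own policy in 5.2.1.2.

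**What to change.** 1. In 4.7.1.1, change both limbs of the combined criterion to Grade 3 or higher ALT (>5 × ULN), with no upper limit.
2. Add an operative bullet to 4.7.1.1: in Part 2c, RO7062931 (and PEG-IFN where given) must be permanently discontinued when the 5.2.1.2 criteria for an ALT flare with declining liver function are met. This settles the direct-bilirubin, albumin and symptom differences, which step 1 alone leaves open.
3. In 5.2.1.2, state that interrupt-and-reconsider for isolated ALT above 10 × ULN applies to Part 2c only, since 4.7.1.1 requires discontinuation for confirmed ALT ≥ 10 × ULN in Parts 2a/2b.
4. Use one boundary, ≥10 or >10 × ULN, in both sections.

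The cost is protocol wording only, with no extra tests or visits. Isolated ALT elevation in Part 2c stays outside the mandatory list, as the waiver intends.
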